4.3 Handling of repeated and unscheduled measurements

All repeated and unscheduled measurements will be presented in the data listings, where applicable. The following general rules will apply to all repeated and unscheduled measurements:

- For repeated measurements obtained prior to the first dose of study medication, the latest value (which may be scheduled or unscheduled) will be used in the calculation of the descriptive statistics
- For repeated measurements obtained at the designated Baseline visit, the latest value (which may be scheduled or unscheduled) will be defined as the Baseline provided that this occurred prior to the first dose of study medication
- Unscheduled and repeated measurements will not be used in the descriptive statistics at time points after first dose of study medication
- Unscheduled measurements performed for the Early Withdrawal (EW) visit will be assigned to the EOS visit (Section 4.4) and analyzed accordingly as an EOS visit.

4.4 Handling of measurements obtained at the early withdrawal visit

Subjects who withdraw early from the study for any reason, including those withdrawn from study medication, will be asked to return for the EOS Visit 7 to 10 days after last intake of study

medication and will then enter the SFU Period and will undergo the same assessments performed at the EOS Visit.

4.5 Interim analyses and data monitoring

Not applicable, there is no interim analysis and no data monitoring planned for this study.

4.6 Multicenter studies

Not applicable, this is a single center study.

4.7 Multiple comparisons/multiplicity

Not applicable.

4.8 Use of an efficacy subset of subjects

Not applicable.

4.9 Active-control studies intended to show equivalence

Not applicable.

4.10 Examination of subgroups

Not applicable.

5 STUDY POPULATION CHARACTERISTICS

5.1 Subject disposition

The number of subjects who were enrolled into the study, subjects who completed or prematurely discontinued the study, as well as the reason for discontinuation, will be summarized for all subjects, based on the FAS. A subject who completed the study is defined as a subject who completed all visits up to and including the SFU.

The number and percentage of subjects who discontinued due to AEs will be summarized separately for all subjects, based on the FAS. This will be used for European Union Drug Regulating Authorities Clinical Trials (EudraCT) reporting.

The number and percentage of subjects included in each of the analysis sets will be summarized for all subjects and for each treatment period based on the ES. Percentages will be calculated based on the FAS for the purpose of this summary.

Screen failure reasons will be summarized for the ES. A listing of subjects who did not meet study eligibility criteria will also be presented for the ES.

In addition, the following listings will be presented:

- Subject disposition (ES)
- Study discontinuation (FAS)
- Visit dates (FAS)
- Subject analysis sets (ES)

The listing of subject disposition will include the date of informed consent, date and time of first and last dose of study medication, date of premature termination and primary reason (if applicable) and date of final contact.

The listing of study discontinuation will include the reason for discontinuation and the number of days on study medication.

The number of days on study medication will be calculated as follows:

$$\begin{aligned} & \text{Number of Days on study medication} \\ & = (\text{Date of Last Dose Received} - \text{Date of First Dose Received}) + 1 \end{aligned}$$

5.2 Protocol deviations

Important protocol deviations will be identified and classified by the deviation types in the IPD document.

A listing of all IPDs identified at the DEM will be presented for all subjects based on the FAS and will include the deviation type and description. The number and percentage of subjects in the FAS with IPDs will be summarized for all subjects and for each treatment period for each deviation type. The denominator for the percentages will be the number of subjects in the FAS.

6 DEMOGRAPHICS AND OTHER BASELINE CHARACTERISTICS

6.1 Demographics

A by-subject listing of demographics will be presented based on the ES. This will include the date of birth, age (in years), sex, race, ethnicity, height (in cm), weight (in kg) and body mass index (BMI). The body weight will be the measurement obtained at Screening.

Body mass index in kg/m^2 is calculated based on the height (in m) and the weight (in kg) using the following formula:

$$BMI(\text{kg}/\text{m}^2) = \text{weight}(\text{kg})/[\text{height}(\text{m})]^2$$

The BMI will be reported to 1 decimal place.

All demographic characteristics (except for date of birth) will be summarized by for all subjects based on the FAS. The summary of age will include descriptive statistics and categorical summaries, the latter based on requirements for European Union Drug Regulating Authorities Clinical Trials (EudraCT) and clinicaltrials.gov reporting.

For the EudraCT reporting, the categories will include:

- 18 to <65 years
- 65 to <85 years
- ≥ 85 years

For clinicaltrials.gov reporting, the categories will include:

- ≤ 18 years
- 19 to <65 years

- ≥ 65 years

6.2 Other Baseline characteristics

Lifestyle information (alcohol, tobacco, illicit drug use and caffeinated beverage use) will be listed and summarized for all subjects in the FAS.

6.3 Medical history and concomitant diseases

Medical history will be listed and summarized (in an incidence table) for the FAS for all subjects, by MedDRA system organ class (SOC) and preferred term (PT). The reported term will be included in the listing. The summary will include the number and percentage of subjects, and will be sorted alphabetically by SOC and by descending incidence of PT within each SOC, based on the 'All Subjects' column.

Procedure history will be listed separately by the procedure reported term based on the FAS. Concomitant medical procedures occurring during the study will be listed for the FAS.

6.4 Prior and concomitant medications

Prior and concomitant medications will be listed and summarized for all subjects in the FAS, by WHODD Anatomical Main Group [Level 1 term text], Pharmacological Subgroup [Level 3 term text] and PT. The reported term will be included in the listing. Separate tabulations will be presented for prior medications and concomitant medications. Prior medications which continued into the treatment period will also be classified as concomitant and will be included in both summaries. Concomitant medications will be described for all subjects and for each treatment period based on the FAS.

All tabulations will be sorted alphabetically by Level 1 term, alphabetical Level 3 term within Level 1 and decreasing frequency of PT in the 'All Subjects' column.

6.4.1 Prior medication definition

Prior medications include any medications that started prior to the date of first dose of PSL. This includes medications that started prior to the first dose of PSL and continued after.

6.4.2 Concomitant medication definition

Concomitant medications are medications taken at least one day in common with the study IMP (after dosing with PSL) and/or the Safety Follow-Up Period.

If a medication is started prior to PSL administration and stopped after, that medication will be classified as both prior and concomitant

Any medications with missing dates and/or times will be handled as described in [Section 4.2.4](#) to classify them as prior or concomitant.

7 MEASUREMENTS OF TREATMENT COMPLIANCE

Administration of PSL or erythromycin will be performed under the supervision of the Investigator (or designee), and the Investigator (or designee) will check the study participant's hands and the oral cavity immediately after dosing to confirm ingestion of the study medication. Compliance will be monitored by drug accountability and by drug assay for PSL (using the drug concentration in the blood/plasma). Compliance with the study medication is defined as consumption by the study participant that confirms 100% with the planned dosage.

Drug administration/consumption will be recorded and any discrepancies with the dosing regimen will be explained. Dosing deviations will be included in the listing of IPDs where applicable.

No formal calculations of compliance will be presented as all study medication is administered on site.

8 EFFICACY ANALYSES

Not applicable.

9 PHARMACOKINETICS

The calculation of the PK parameters of PSL and its metabolites (██████████ for both plasma conventional venous and MITRA dried blood and ██████████ for venous sampling only) will be performed by the Quantitative Clinical Development Department, PAREXEL. All PK TFLs will be produced by PAREXEL Biostatistics (Early Phase).

Pharmacokinetic concentrations and PK parameters will be summarized by treatment ie PSL with (Period 3b) and without erythromycin (Periods 1 and 2 separately), using the PK-PPS and listed on the FAS by treatment and subject. Figures of summaries will be based on the PK-PPS and figures of individual concentrations will be based on the FAS.

Pharmacokinetic parameters of PSL and metabolites (██████████ for both plasma conventional venous and MITRA dried blood and ██████████ for venous sampling only) will be calculated using the actual blood sampling times.

9.1 Analysis of the primary pharmacokinetic variables

Individual plasma concentrations of PSL (from conventional venous sampling) will be listed by treatment period (PSL: Period 1; PSL: Period 2; PSL+ Erythromycin: Period 3b) and will include the actual and nominal sampling times and the deviation between them. All deviations will be calculated relative to the first dose of study medication in that period. Any samples that are obtained outside the tolerance window permitted at the specified time point will be discussed at the DEM and any possible exclusion from analysis will be documented accordingly. The primary PK variables in plasma are: C_{max} and $AUC_{(0-12)}$ following a single dose and $C_{max,ss}$ and AUC_{τ} following multiple doses of PSL.

The PK plasma concentrations and primary PK parameters of PSL will be summarized by treatment period and nominal sampling times using descriptive statistics (number of available observations (n), arithmetic mean, median, SD, minimum, maximum, geometric mean, geometric CV and 95% CI for the geometric mean (assuming lognormally distributed data)). Values below the LLOQ will be reported with a clear sign indicating that they were below the LLOQ.

Individual subject concentration-time profiles of PSL will be displayed graphically in linear and semi-logarithmic scale. Combined individual (spaghetti) plots will be displayed by treatment period with all subjects overlaid on the same plot (linear and semi-logarithmic scale).

Geometric mean profiles of plasma concentrations for PSL over time will be presented, with all treatment periods overlaid on the same plot, in both linear and semi-logarithmic scale. For the

linear scale plot only, the lower and upper 95% confidence interval (CI) for the geometric mean will be displayed.

All plasma concentration figures will include the LLOQ on the semi-logarithmic scale plots and will be based on scheduled times.

The primary comparison of interest is the similarity of plasma PK parameters (C_{max} , $AUC_{(0-12)}$, $C_{max,ss}$, and AUC_{τ}) for PSL between treatment periods with erythromycin (Treatment Period 3b) and PSL without erythromycin (treatment periods 1 and 2). This will be assessed using a linear mixed effects model with treatment periods (1, 2 and 3b, comparing with vs without erythromycin periods) fitted as fixed effects and subject fitted as a random effect. The mixed effects model will be using Kenward-Rodgers degrees of freedom. Point estimates for the ratio of geometric means with and without erythromycin (Period 3b compared to periods 1 and 2) and the respective 2 sided 90% CIs will be computed using the least squares means and the root mean squares of error from the mixed effects model, based on of the log-transformed data with subsequent exponential transformation. In addition point estimates for the ratio of geometric means and the respective 2 sided 90% CIs will be presented for the following comparisons:

- Treatment Period 1 (PSL) compared to Treatment Period 3b (PSL + erythromycin)
- Treatment Period 2 (PSL) compared to Treatment Period 3b (PSL + erythromycin)

Treatment Period 1 (PSL) compared to Treatment Period 2 (PSL) Ping pong plots will be displayed for each of the PK parameters (C_{max} , $AUC_{(0-12)}$, $C_{max,ss}$, and AUC_{τ}) against treatment of PSL with (Treatment Period 3b) and without erythromycin (treatment periods 1 and 2, separately).

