### **5.3.1 Venous blood**

Venous blood samples for PK analysis will be performed as follows:

- Predose and 0.25h, 0.5h, 0.75h, 1h, 1.25h, 1.5h, 2h, 3h, 4h, 6h, 8h, and 12h post first dose of PSL during each Treatment Period (Day 1, Day 12, and Day 26)
- Predose and 0.25h, 0.5h, 0.75h, 1h, 1.25h, 1.5h, 2h, 3h, 4h, 6h, 8h, 12h, 24h, 36h, 48h, and 72h post last dose of PSL during Treatment Period 1 (Day 5) and Treatment Period 2 (Day 16)

- Predose and 0.25h, 0.5h, 0.75h, 1h, 1.25h, 1.5h, 2h, 3h, 4h, 6h, 8h, 12h, 24h, 36h, 48h, 60h, 72h, 96h, and 120h post last dose of PSL during Treatment Period 3b (on the morning of Day 33)

Additional PK trough samples will be taken immediately prior to each morning dose of PSL during Treatment Period 1 (Day 2 through Day 4) and Treatment Period 2 (Day 13 through Day 15) and each morning combination dose during Treatment Period 3b (Day 27 through Day 33).

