**Table 9–1: Irrelevant time deviations for PK sampling**

PK blood sampling times	Deviation from scheduled time considered irrelevant
0 hours (predose)	Within 60 minutes
0.25 to 1.5 hours	2 minutes
2 to 8 hours	5 minutes
12 hours	15 minutes
24 to 48 hours	60 minutes

PK=pharmacokinetic

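### SAP 9.1 measures every PK sampling-time deviation from the first dose of the period, although the steady-state profiles and troughs are scheduled from later doses

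*SAP*

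**What the plan says.** SAP 9.1 lists each venous PSL concentration with its actual time, its nominal time and the difference between them. It fixes one reference for that difference: "All deviations will be calculated relative to the first dose of study medication in that period". The result has a use: "Any samples that are obtained outside the tolerance window permitted at the specified time point will be discussed at the DEM", where exclusion may follow.

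The protocol (5.3.1) uses three references:

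- The Day 1, 12 and 26 profiles are timed from the first PSL dose of the period.
- The second profile is timed from the final PSL dose. For Periods 1 and 2 the list ends "12h, 24h, 36h, 48h, and 72h post last dose of PSL during Treatment Period 1 (Day 5) and Treatment Period 2 (Day 16"; for Period 3b it reads "post last dose of PSL during Treatment Period 3b (on the morning of Day 33".
- Troughs follow each day's own dose: "Additional PK trough samples will be taken immediately prior to each morning dose of PSL during Treatment Period 1 (Day 2 through Day 4", with matching wording for Periods 2 and 3b.

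Footnotes q and r of Table 5-1 agree with this.

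Protocol Table 9–1 supplies the windows under the column title "Deviation from scheduled time considered irrelevant": 60 minutes predose, 2 minutes from 0.25 to 1.5 h, 5 minutes from 2 to 8 h, 15 minutes at 12 h, and 60 minutes from 24 to 48 h. It has no row for 60, 72, 96 or 120 h.

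**The concern.** A deviation is meaningful only if actual and nominal time are counted from the same dose. For the steady-state profiles and troughs, the SAP counts actual time from one dose and the protocol schedules the sample from another. No other section of either document corrects the reference, and SAP 3.9 (changes to protocol-defined analyses) does not mention it.

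The Day 5, 16 and 33 profiles supply Cmax,ss and AUCτ, two of the four primary variables. AUCτ is also the variable on which the sample size is based (SAP 2.4). If the deviation is wrong, the meeting that decides on exclusions is shown samples that were taken on time and may not be shown samples that were not.

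**Working it through.** The plan states no figure to reproduce, so the check applies its own schedule and windows to the rule as written.

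**1. Samples by reference dose** (venous, per participant; Protocol 5.3.1)

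| | First-dose profile | Last-dose profile | Separate troughs | Total |
|---|---|---|---|---|
| Period 1 | 13 | 17 | 3 | 33 |
| Period 2 | 13 | 17 | 3 | 33 |
| Period 3b | 13 | 20 | 6 | 39 |
| All | 39 | 54 | 12 | 105 |

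The Day 33 trough is counted once, as the predose sample of that profile. Samples scheduled from a later dose: 54 + 12 = 66 of 105 (63%).

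**2. What the rule yields.** Let N be the nominal interval from the first dose of the period to the dose from which the sample is scheduled. Let t be the scheduled time after that later dose, e the true deviation, and d the shift in clock time between the two doses. The sample is then taken N + d + t + e after the first dose.

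- If nominal time stays as t, the listed deviation is N + d + e. For Days 5 and 16, N = 4 × 24 = 96 h. For Day 33 counted from Day 26, N = 7 × 24 = 168 h.
- If nominal time is restated as N + t, the listed deviation is d + e.

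Neither equals e unless d = 0, and the first does not even then.

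**3. False flags on the second reading.** Set e = 0, so the listed deviation is d. The 12 post-dose samples up to 12 h comprise 6 with a 2-minute window (0.25 to 1.5 h), 5 with a 5-minute window (2 to 8 h) and 1 with a 15-minute window (12 h).

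| Shift d | Flagged, of 12 |
|---|---|
| 1 min | 0 |
| 3 min | 6 |
| 6 min | 6 + 5 = 11 |
| 10 min | 11 |
| 16 min | 12 |

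Above 60 minutes, the predose and 24 to 48 h samples are flagged as well.

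**4. Masking.** Take a sample drawn 10 minutes late (e = +10) after a dose given 10 minutes earlier by the clock than the first dose (d = −10). The listed deviation is 0.

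**5. How many of the 66 are practically exposed.** There are three steady-state profiles.

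- 2-minute window: 3 × 6 = 18
- 5-minute window: 3 × 5 = 15
- 15-minute window: 3 × 1 = 3
- 60-minute window: 3 predose + 12 troughs + 9 at 24 to 48 h = 24 (troughs placed under the predose row)
- no window in Table 9–1: 3 at 72 h + 1 each at 60, 96 and 120 h = 6

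So 36 samples have a tight window, and 24 + 6 = 30 do not.

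**6. Size of d.** Morning doses may fall anywhere from 7 to 10 AM (Protocol 5.2.2, 8.2, 8.4), so d can reach 180 minutes. The site is asked to make every effort to keep each participant's times constant, but no tolerance is set. The documents give no distribution for d, and therefore no expected flag rate.

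**7. Which dose opens Period 3.** SAP 9.1 and 3.6 name Period 3b for PK, which points to Day 26. The rule, however, refers to study medication, and SAP 4.2.1 uses Day 23 as the predose day of Period 3. Counted from the Day 23 erythromycin dose, even the Day 26 profile is 3 × 24 = 72 h off its reference.

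**The case against.** The best defence is that the sentence defines a listing column and nothing more. Parameters are calculated from actual sampling times (Protocol 9.1 and 12.3.1, SAP 9), and concentration summaries and figures use nominal or scheduled times. A reader might infer that Cmax,ss and AUCτ would be miscalculated; the documents do not support that.

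A reader might also infer that flagged samples drop out automatically. They do not: they are "discussed at the DEM and any possible exclusion from analysis will be documented accordingly". Table 9–1 says which deviations are irrelevant, not which ones require exclusion. Every dose time is listed (SAP 10.1), and one dosing shift moves a whole profile by the same amount, so an attentive meeting could recognise the pattern. An error of 96 h or 168 h would be hard to miss.

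A third inference is that, because steady-state samples are judged more harshly than single-dose samples, the primary result is biased. The primary analysis (SAP 9.1) compares the same parameter between Period 3b and Periods 1 and 2, and the rule treats the steady-state profile alike in all three. No bias in the ratio with versus without erythromycin follows.

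Finally, 66 of 105 overstates the practical exposure, since small shifts seldom matter for the 30 samples with a 60-minute window or none. The 3-hour dosing window is the permitted range, not the shift to expect within a participant.

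All of this stands as a limit on impact. None of it makes the rule correct. Programmed as written, the listing is wrong; programmed sensibly, it departs from the SAP.

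**Conclusion.** The reference dose is wrong as written for the steady-state profiles and the troughs. If nominal times are kept as hours after the last dose, the error is about 96 h or 168 h. If they are restated from the first dose, the error is the dosing shift, and the windows are narrow enough that shifts of 3, 6 and over 15 minutes falsely flag 6, 11 and 12 of the 12 post-dose samples per 0–12 h profile. These counts assume perfectly timed samples and one shift per profile; they assume no distribution for the shift.

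The samples practically exposed are the 36 with windows of 2, 5 or 15 minutes. The consequence is a wrong deviation listing and wrong triggers, in both directions, for discretionary exclusion of samples behind Cmax,ss and AUCτ. Direct miscalculation of these variables, automatic loss of data and bias in the erythromycin ratio are not shown. The point is worth correcting because it touches primary data and costs almost nothing.

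**What to change.** Replace the sentence in SAP 9.1 with: *Deviations will be calculated relative to the PSL dose to which the nominal time refers (for predose and trough samples, the dose that follows).*

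A sample taken on time then has deviation 0 whatever the dosing shift, and the choice between Day 23 and Day 26 as the Period 3 reference no longer arises.

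The cost is one sentence and a small programming change. Dose dates and times are already listed under SAP 10.1, so no new data are needed. SAP Section 1 requires an amendment when analysis definitions change before database lock, so the correction should be made before the lock and before the deviation listing goes to the data evaluation meeting. The missing windows for the 60, 72, 96 and 120 h samples are a separate gap that this sentence does not close.

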9.2 Analysis of secondary pharmacokinetic variables

The secondary PK variables in plasma for PSL are: t_{max} , and C_{min} following single dose and t_{max} , $t_{1/2,ss}$, λ_z , C_{trough} , and CL/F_{ss} following multiple doses, C_{max} , $AUC_{(0-12)}$, $C_{max,ss}$, and AUC_{τ} for PSL metabolites (), and the metabolite-to-parent ratios for C_{max} , $AUC_{(0-12)}$, and AUC_{τ} .

Additionally, the secondary PK variables in urine for PSL and its metabolites () are: CL_r , A_e , f_e , and CL_{form} in urine following a single dose and multiple doses.

Urine amount, time profiles and PK parameters of PSL and metabolites in urine will be summarized and plotted as described in Section 9.1. Urine concentration and amount excreted will be listed for PSL and the three metabolites.

Each of the secondary PK variables, for PSL and its metabolites in plasma, will be summarised by treatment period using the same descriptive statistics as for the plasma concentrations and PK variables in Section 9.1, and plotted in a similar manner.

The mixed effect model described in Section 9.1 will be applied for the PK variables C_{max} , $AUC_{(0-12)}$, $C_{max,ss}$, and AUC_{τ} for the two PSL metabolites () in plasma (conventional venous of sampling). Point estimates for the ratio of geometric means and the respective 2 sided 90% CIs will be computed using the least squares means and the root mean squares of error from the mixed effects model, based on of the log-transformed

data with subsequent exponential transformation for the same comparisons than those described in [Section 9.1](#).

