#### 3.2 Secondary objectives

The secondary objectives of this study are to:

- Assess the safety and tolerability of PSL in the presence and absence of erythromycin in healthy study participants
- Evaluate and compare the plasma PK of PSL metabolites, [REDACTED] in the presence and absence of erythromycin in healthy study participants
- Assess and compare the urine PK of PSL and its metabolites [REDACTED] and [REDACTED] in the presence and absence of erythromycin in healthy study participants

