### **12.3 Planned pharmacokinetic and other analyses**

#### **12.3.1 Analysis of the primary pharmacokinetic variables**

Pharmacokinetics will be determined using the PK-PPS.

Pharmacokinetic parameters of PSL and metabolites will be calculated by using the actual blood sampling time points.

The plasma concentration time profiles (and urine amounts) and PK parameters of PSL and metabolites will be summarized by treatment periods using descriptive statistics (number of available observations, arithmetic mean, SD, geometric mean, coefficient of variation of the geometric mean, median, minimum, and maximum). Values below the lower limit of quantification (LLOQ) will be reported with a clear sign indicating that they were below the

LLOQ. Descriptive statistics of concentrations will be calculated if at least two-thirds of the individual data points are quantifiable ( $\geq$ LLOQ).

Individual plasma PSL and metabolites concentration time profiles will be displayed graphically on a linear-linear scale and semi-logarithmic scale (including spaghetti plots). Geometric mean plasma concentrations-time curves including 95% confidence intervals (CIs) will be displayed by treatment period (without/with erythromycin).

The similarity of PK parameters for PSL and its metabolites ( $C_{max}$ ,  $AUC_{(0-12)}$ ,  $C_{max,ss}$ , and  $AUC_{\tau}$ ) between periods with erythromycin and without erythromycin will be assessed within the analysis of variance (ANOVA) using data from the 3 treatment periods as follows: point estimates for the ratio of geometric means between with and without erythromycin and the respective 2-sided 90% CIs will be computed using the least squares means and the root mean squares of error from the ANOVA of the log-transformed data with subsequent exponential transformation. Inter-study participant and intra-study participant variability on PK parameters for PSL and its metabolites will be derived from these analyses. Ping pong plots will be displayed.

The PSL concentrations and PK parameters obtained from MITRA microsampling method will be compared to those of the conventional venous sampling method using descriptive analysis (tables with summary statistics and graphs).

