3.9 Changes to protocol-defined analyses

The protocol states that MITRA dried blood microsampling method will be compared to those of the plasma conventional venous sampling method using descriptive analysis (tables with summary statistics and graphs). Nonetheless, as described in [Section 9.3](#), the exploratory analysis will also be described using linear mixed effects model.

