13 APPENDICES

13.1 Breakdown of treatment periods reported into the TFLs by study assessment data

Table 13.1: Breakdown of treatment periods reported into the TFLs by study assessment data

Treatment	PSL		PSL	Erythromycin pre	PSL + Erythromycin	Erythromycin post	EOS/SFU	All subjects
	Period 1	Period 2	Period 1 + 2	Period 3a	Period 3b	Period 3c		
Subject disposition	X	X		X	X	X	X	
Protocol deviations	X	X		X	X	X	X	
Demographics								X
Medical history								X
Lifestyle								X
Prior/concomitant medications								X
Adverse Events			X	X	X	X	X	
Laboratory tests	X	X			X	X	X	
Other safety continuous measurements (vital signs, ECG)	X	X		X	X	X	X	
Safety categorical results (laboratory shift tables, PDILI)	X	X			X	X		
PK plasma and urine for PSL and metabolites	X	X			X			

ECG=electrocardiogram; EOS=end of study; PK=pharmacokinetic; PSL=Padsevonil; SFU=Safety Follow-up.

Note: Period refers to the treatment period.

14 **AMENDMENT(S) TO THE STATISTICAL ANALYSIS PLAN**

Not Applicable

This document cannot be used to support any marketing authorization application and any extensions or variations thereof.

REDACTED COPY

STATISTICAL ANALYSIS PLAN SIGNATURE PAGE

This document has been reviewed and approved per the Review and Approval of Clinical Documents Standard Operating Procedures. Signatures indicate that the final version of the SAP or amended SAP is released for execution.

This document cannot be used to support any marketing authorization application and any extensions or variations thereof.

REDACTED COPY

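### Urine PK is to be compared with and without erythromycin, but the plan gives period summaries only and no within-participant ratio with a confidence interval

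*SAP*

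**What the plan says.** **Objective.** Protocol Section 3.2, repeated in SAP Section 2.1.2: "Assess and compare the urine PK of PSL and its metabolites", with and without erythromycin. The objective for the plasma metabolites also asks for a comparison.

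**Urine variables.** SAP Section 9.2 names CLr, Ae, fe and CLform, "in urine following a single dose and multiple doses".

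**Urine analysis.** SAP Section 9.2: "Urine amount, time profiles and PK parameters of PSL and metabolites in urine will be summarized and plotted as described in Section 9.1". Urine concentrations and amounts are also listed. Protocol Section 12.3.1 is descriptive too: "The plasma concentration time profiles (and urine amounts) and PK parameters of PSL and metabolites will be summarized by treatment periods using descriptive statistics".

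**Where the model applies.** SAP Section 9.1 sets up the model and limits it to plasma PSL: "The primary comparison of interest is the similarity of plasma PK parameters". Section 9.2 extends it: "The mixed effect model described in Section 9.1 will be applied for the PK variables" Cmax, AUC(0-12), Cmax,ss and AUCtau of two metabolites in plasma, with geometric mean ratios and 90% CIs. Section 9.3 adds variability estimates for the same four parameters and a MITRA-versus-venous model. SAP Section 3.9 records one change from the protocol, for MITRA: "the exploratory analysis will also be described using linear mixed effects model".

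**Whether urine is measured.** Protocol Section 9.2.2 stores the urine aliquots and makes their assay depend on the blood PK results.

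**The concern.** The plasma-metabolite and urine objectives both ask for a with/without comparison. The plasma metabolites get a within-participant ratio with a 90% CI; urine gets separate summaries for each period. Those summaries do not report the within-participant correlation, so the uncertainty of the with/without ratio cannot be recovered from them.

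The design supplies what is needed. Under SAP Section 3.6 all participants follow the same fixed sequence, so each is due to contribute PSL alone twice and PSL with erythromycin once. CLform is of particular interest. Protocol Section 2.1 says the two major metabolites are formed mainly through CYP3A4, the enzyme erythromycin inhibits, and CLform measures metabolite formation.

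Dropout adds a smaller difficulty. Up to 28 participants are enrolled to obtain 20 completers, and the PK-PPS requires only one determinable PK parameter. The period geometric means may therefore rest on partly different participants.

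**Working it through.** **1. Is a urine contrast planned anywhere?**

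| Place | Provision for urine |
|---|---|
| Protocol 12.3.1 | Descriptive statistics by period; ANOVA limited to Cmax, AUC(0-12), Cmax,ss, AUCtau |
| SAP 9.1 | Model and ping pong plots named for those four plasma parameters only |
| SAP 9.2 | Summaries, plots and listings; model invoked separately, for plasma metabolites |
| SAP 9.3 | Variability and MITRA analyses; nothing for urine |
| SAP 3.9 | Only the MITRA model is added |
| SAP Table 13.1, row "PK plasma and urine for PSL and metabolites" | Periods 1, 2 and 3b |

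The Table 13.1 row is neutral, because plasma shares it and does have contrasts elsewhere. The other entries agree: no ratio, difference or CI is planned for CLr, Ae, fe or CLform.

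**2. The plan's own figure.** The only sample-size figure is 20 completers, for plasma AUCtau (protocol Section 12.7). Taking the CV of 140% directly as an SD of 1.4, the SD of a paired difference is 1.4 × √(2 × (1 − 0.5)) = 1.4. The smallest n for which a 95% CI has half-width at most 0.75 with conditional probability of at least 0.80 is 20 (probability 0.829; 0.769 at n = 19). The figure reproduces on that reading. It says nothing about urine and is used below only as the number of completers.

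**3. What the Section 9.1 contrast would give.** The documents state no urine CV or correlation, so both are assumptions and are varied. Let s = √ln(1 + CV²) be the log-scale SD, ρ the between-period correlation, and n = 20.

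- Period 3b against the mean of Periods 1 and 2: SE = s × √(1.5(1 − ρ)/n), on 2(n − 1) = 38 df.
- Two period summaries read as independent samples: SE = s × √(2/n), on 2n − 2 = 38 df.
- In both cases t(0.95, 38) = 1.686, and the 90% CI is the ratio ×/÷ exp(t × SE).

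Example at CV 50%, ρ = 0.5: s = √ln 1.25 = 0.472. The contrast gives exp(1.686 × 0.472 × √0.0375) = 1.17. The independent reading gives exp(1.686 × 0.472 × √0.1) = 1.29.

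| CV (assumed) | Section 9.1 contrast, ρ = 0.5 | Read as independent |
|---|---|---|
| 30% | ×/÷ 1.10 | ×/÷ 1.17 |
| 50% | ×/÷ 1.17 | ×/÷ 1.29 |
| 100% | ×/÷ 1.31 | ×/÷ 1.56 |
| 140% | ×/÷ 1.41 | ×/÷ 1.74 |

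At ρ = 0.5 the SE ratio is √(0.0375/0.1) = 0.61, so the log-scale interval is about 39% narrower whatever the CV. At CV 50%, ρ from 0.3 to 0.9 moves the contrast from ×/÷ 1.20 to ×/÷ 1.07, against 1.29.

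The 39% combines two gains: pairing, and use of both reference periods. Pairing Period 3b with one reference period, at CV 140% and ρ = 0.5, gives exp(1.729 × 1.042 × √(1/20)) = 1.50 on 19 df, about 27% narrower than 1.74.

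**4. Is there a common interval?** After the first dose, urine is collected over 0–12 h in every period. After the last dose, collection runs to 48 h in Periods 1 and 2 but to 96 h in Period 3b (protocol Section 5.3.3). SAP Section 2.2.1.2 gives no interval for Ae. Total Ae after the last dose is therefore not comparable across periods, whereas 0–12 h is. It also matches the 12-hour AUCs used as denominators for CLr and CLform.

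**The case against.** **The protocol already chose description.** Section 12.3.1 plans descriptive statistics for urine, and the SAP follows it. The same section uses the language of comparison for MITRA against venous sampling while specifying descriptive methods, so an objective to compare does not by itself require a model. This stands: the gap begins in the protocol, and the SAP does not depart from it. But the SAP did raise the exploratory MITRA comparison to a model, which leaves a secondary objective with less than an exploratory one.

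**An estimate can be read off.** A reader might infer that the urine objective ends with no estimate at all. The documents do not support that. Geometric means by period are planned, and with complete data their ratio equals the within-participant geometric mean ratio. PK parameters are also listed by participant (SAP Section 9). What is missing is a planned ratio with its CI, and a rule that handles incomplete participants.

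**The cross-reference to Section 9.1 may carry more.** It could be stretched to cover the ping pong plots or even the model. Section 9.1 names those plots for the four plasma parameters only, and a plot gives no interval. Section 9.2 goes on to invoke the model explicitly for plasma metabolites, which would be unnecessary if the urine sentence already included it.

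**The plasma results address the pathway, and urine may not be assayed.** Both points are fair and lower the importance. The conditional assay decides whether data exist, not how they should be analysed.

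**Conclusion.** The point holds as a modest improvement. A stated secondary objective has no planned within-participant ratio with a CI, although the design provides the data and the SAP already uses the method for plasma. At 20 completers and a correlation of 0.5, the contrast is about 39% narrower on the log scale than two period summaries read as independent.

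The absolute widths rest on assumed urine CVs. It would be tempting to quote only the CV of 140%, but that is the planning value for plasma PSL AUCtau and the documents do not extend it to urine. The independent reading is likewise a benchmark for what a reader of the tables could do, not an analysis the SAP plans. Nothing here affects the primary analysis or the sample size.

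**What to change.** In SAP Section 9.2, state that if urine is assayed the Section 9.1 mixed model will be fitted to the logs of:

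- Ae over 0–12 h, for PSL and the metabolites;
- CLr over the same interval, for the analytes for which Section 2.2.1.2 defines it;
- CLform, for metabolites only, since it is not defined for PSL.

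Fit first-dose days (1, 12, 26) and last-dose days (5, 16, 33) separately. Report the geometric mean ratio of Period 3b to Periods 1 and 2 with its 90% CI, labelled as estimation. fe needs no model of its own: it is Ae multiplied by a constant (dose and molecular weights), so its ratio equals that of Ae. State in Section 2.2.1.2 the interval over which Ae is cumulated, and say what will be reported if urine is not assayed.

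Cost: an SAP amendment, reuse of the existing model code and a few more tables. No new samples or visits are needed.
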